2.2 Secondary Objectives

- 2.2.1 To characterize the changes in neoantigen expression and T cell receptor (TCR) clonality in blood and tumor samples after treatment with pembrolizumab alone and the combination of pembrolizumab and entinostat.
- 2.2.2 To evaluate the changes in STAT and NF-κB gene signatures and histone acetylation (H3K9Ac, H3K27Ac, and others) levels after combination treatment with pembrolizumab and entinostat as compared to pembrolizumab alone (subset of subjects with frozen pre- and post-treatment tumor tissue available).
- 2.2.3 To document safety, tolerability, and feasibility of preoperative administration of pembrolizumab with and without entinostat in cisplatin-ineligible MIBC patients prior to scheduled surgical resection, and to document safety, tolerability and feasibility of pembrolizumab with and without entinostat prior to trimodality therapy in MIBC patients (National Cancer Institute Common Terminology for Adverse Events [NCI-CTCAE v5.0]).
- 2.2.4 To define the pathologic response rate (<pT2) and pathologic complete response rate (pT0) after treatment with pembrolizumab alone and the combination of pembrolizumab and entinostat in cisplatin-ineligible subjects undergoing radical cystectomy
- 2.2.5 To estimate the clinical complete response rate (cT0) after treatment with pembrolizumab alone and the combination of pembrolizumab and entinostat in patients undergoing maximal TURBT prior to chemoradiation
- 2.2.6 To estimate the event free survival (EFS) after treatment with pembrolizumab alone and the combination of pembrolizumab and entinostat in patients with MIBC

- 2.2.7 To estimate overall survival (OS) after treatment with pembrolizumab alone and the combination of pembrolizumab and entinostat in patients with MIBC
- 2.3 Exploratory Objectives

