3.2 Secondary Endpoints

- **3.2.1** Pre- and post-treatment TCR repertoire and neoantigen changes will be defined by changes in TCR clonality and neoantigen load.
- 3.2.2 Pre- and post-treatment changes in STAT and NF-κB expression will be evaluated using mRNAseq analysis and changes in histone acetylation (H3K9Ac and H3K27Ac) levels in a subset of subjects with pre- and post-treatment tumor tissue available (diagnostic TURBT and maximal TURBT or cystectomy tissue available)
- 3.2.3 Toxicity will be evaluated according to guidelines from National Cancer Institute

 Common Terminology for Adverse Events (NCI-CTCAE) criteria version 5.0
 and include all adverse events continuing or occurring 30 days after completion of treatment
- **3.2.4** A pathologic response will be defined as <pT2 (pT0-T1N0M0) and pathologic complete response will be defined as pT0N0M0 at the time of cystectomy at the completion of study treatment.
- 3.2.5 The clinical complete response rate (cT0) is defined as cT0 at the time of maximal TURBT
- **3.2.6** EFS is defined as day 1 of neoadjuvant/protocol treatment to date of first documentation of disease progression (or until recurrence after surgery or radiation) or death due to any cause. Recurrence includes the development of second primary muscle-invasive urothelial malignancies.
- **3.2.7** Overall survival is defined as day 1 of neoadjuvant/protocol treatment to date of death due to any cause. Patients will be censored at date of last follow-up.

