8.2 Post-Treatment Surgery

Post-treatment surgery (either cystectomy or maximal TURBT for trimodality patients) should occur within 10 weeks of the initiation of study therapy. For cystectomy subjects, the surgery with curative intent will occur as per routine clinical standard of care and will be performed at the discretion of the surgeon. For subjects undergoing trimodality therapy, maximal TURBT should occur within 10 weeks of initiation of study therapy, followed by initiation of standard of care concurrent chemotherapy and radiation.

Tissue acquisition: A sample of tumor tissue from the post-treatment surgery will be preserved for correlative studies. A sample of lymph node tissue from the lymph node dissection, if available, and normal tissue from the cystectomy specimen will be preserved for correlative studies from all cystectomy subjects. These tissues will be preserved in consultation with surgical pathology, and tissue released for correlative studies post pathological review. Note: Subjects who do not complete clinical trial treatment for whatever reason other than withdrawal from the study, but still undergo surgery, will be requested to participate in correlative studies.

Blood sample for correlative studies: blood will be collected in ACD tubes (see Study Laboratory Manual for details).

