9.0 ADVERSE EVENTS

9.1 Definitions

9.1.1 Adverse Event (AE)

An adverse event (AE) is any untoward medical occurrence (e.g., an abnormal laboratory finding, symptom, or disease temporally associated with the use of a drug) in a subject or clinical investigation subject administered a pharmaceutical product and which does not necessarily have a causal relationship with this treatment. An AE can therefore be any unfavorable and unintended sign (including an abnormal laboratory finding), symptom, or disease temporally associated with the use of a medicinal product, whether or not related to the medicinal product.

Hospitalization for elective surgery or routine clinical procedures that are not the result of an AE (e.g., surgical insertion of central line) need not be considered AEs and should not be recorded as an AE. Disease progression should not be recorded as an AE, unless it is attributable by the investigator to the study therapy. Adverse events may occur during the course of the use of Merck product in clinical trials, or as prescribed in clinical practice, from overdose (whether accidental or intentional), from abuse and from withdrawal.

All AEs, SAEs and other reportable safety events that occur after the consent form is signed but before treatment assignment must be reported by the investigator if the event causes the subject to be excluded from the study or is the result of a protocol-specified intervention, including but not limited to washout or discontinuation of usual therapy, diet, or a procedure.

- All AEs from the time of treatment through 30 days following cessation of study therapy must be reported by the investigator.
- All AEs meeting serious criteria, from the time of treatment through 90 days following cessation of study treatment, or 30 days following cessation of study treatment if the participant initiates new anticancer therapy, whichever is earlier must be reported by the investigator.
- All pregnancies and exposure during breastfeeding, from the time of treatment through 120 days following cessation of study treatment, or 30 days following cessation of study treatment if the participant initiates new anticancer therapy must be reported by the investigator.
- Additionally, any SAE brought to the attention of an investigator at any time outside of the time period specified above must be reported immediately by the investigator if the event is considered to be drugrelated.

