9.2 SAEs or Serious SARs

9.2.1 Timing

After informed consent but prior to initiation of study medications, only SAEs caused by a protocol-mandated intervention will be collected (e.g. SAEs related to invasive procedures such as biopsies, medication washout).

For any other experience or condition that meets the definition of an SAE or a serious SAR, recording of the event must begin from day 1 of study treatment and continue through the 30-day follow-up period after treatment is discontinued. Serious adverse events (SAEs) caused by a protocol-mandated intervention, or any grade of events of clinical interest (see section 9.4.2.2) that occur within 90 days of the last pembrolizumab administration must be recorded.

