10.3 Data Analysis Plans

The change in T cell gene signature expression will be calculated for each group (pembrolizumab + entinostat compared to pembrolizumab alone) and compared between groups using a two group t-test. Similar analyses will be done for all gene signatures.

Appropriate descriptive statistics, including median, interquartile range, means, and 95% confidence intervals, will be calculated and reported for all lab values.

The analysis of the toxicity and safety will be based on the frequency of adverse events and their severity. Worst toxicity grades per subject will be tabulated for adverse events and laboratory measurements by using the National Cancer Institute- Common Terminology Criteria for Adverse Events (NCI-CTCAE version 5.0) and will be reported in the form of frequency tables. If 2 subjects have their surgical resection delayed beyond the 10 weeks from the time of initiation of study therapy due to protocol treatment-related adverse events, further enrollment to the study will be halted. Based on the nature and severity of

LCCC 1827 PI: [name], MPH Amendment 6 CONFIDENTIAL UNIVERSITY OF NORTH CAROLINA January 9, 2025

the toxicities observed, consideration will be made to amend the study (if risk of toxicity is felt to be mitigated by protocol amendment) vs terminating the study. If 4 or more patients are delayed due to protocol treatment-related adverse events, then the study will be terminated.

For subjects that undergo cystectomy, the proportion of patients who have a pathologic response to <pT2 will be reported along with a 95% confidence interval. Similarly, the proportion of patients who have a clinical complete response (cT0) will be reported separately for those undergoing cystectomy and trimodality therapy. Patients who progress prior to surgery (unlikely) or do not have surgery will still be included in this estimate and will be considered to have not been downstaged. The Kaplan Meier method will be used to estimate median times, along with 95% confidence intervals, for the secondary objectives of EFS and OS, as defined in Section 3.2.6 and 3.2.7.

Results gathered on these subjects will be highly valuable in providing information that can be used to inform power and sample size considerations for future investigations.

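### The worst-grade adverse-event tables in Section 10.3 can take in operative complications when surgery falls on or before about Day 52, although they are meant to document preoperative drug safety

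*Combined protocol and SAP*

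**What the plan says.** Objective 2.2.3 is to document the safety, tolerability and feasibility of "preoperative administration of pembrolizumab with and without entinostat in cisplatin-ineligible MIBC patients prior to scheduled surgical resection", with a parallel clause for subjects treated before trimodality therapy.

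The endpoint that serves it, 3.2.3, is to "include all adverse events continuing or occurring 30 days after completion of treatment". Section 9.1.1 sets the matching collection rule: "All AEs from the time of treatment through 30 days following cessation of study therapy must be reported by the investigator". It also defines an adverse event without regard to causality.

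The analysis in Section 10.3 is one sentence: "Worst toxicity grades per subject will be tabulated for adverse events and laboratory measurements", reported as frequency tables by CTCAE version 5.0. It does not mention relation to study drug or onset before or after surgery. The same paragraph does use attribution for the surgery-delay rule, which counts delays "due to protocol treatment-related adverse events, further enrollment to the study will be halted".

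Section 8.2 says that the operation "should occur within 10 weeks of the initiation of study therapy". No earliest day is given.

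**The concern.** The objective concerns drug given before an operation, but the window that feeds the tables is tied to the last dose and takes no account of the operation date. A subject who has surgery inside the window contributes postoperative days to it, and a complication in those days is an adverse event under Section 9.1.1.

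The exemptions elsewhere do not remove it. Sections 9.1.1 and 9.1.4 set aside hospitalization for elective or planned procedures. Appendix F (13.6.1) sets aside the procedure itself and surgery already planned before consent. None of them covers a complication of the operation.

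The worst-grade rule sharpens the problem. As a hypothetical case, take a subject with Grade 2 anemia on drug and Grade 3 anemia after cystectomy. The table shows Grade 3 only, and the drug-period grade is lost. What is at stake is how readable a secondary safety summary will be. No test or decision rule depends on it.

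**Working it through.** The plan states no figure for this overlap, so there is nothing to reproduce. The check is calendar arithmetic.

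**Inputs**
- Last planned dose: pembrolizumab on Day 22 in both arms, ±1 day (Section 5.2).
- Adverse-event window: 30 days after treatment (3.2.3, 9.1.1, 9.3). The wording of 3.2.3 is loose; it is read here as running through 30 days, as the other two sections say.
- Surgery limit: 10 weeks from the first dose (8.2).

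**Window end.** 22 + 30 = Day 52. A last dose on Day 21 or 23 moves it to Day 51 or 53.

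**Latest permitted surgery.** 1 + 70 = Day 71.

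**Overlap.** For surgery on day *s*, days in the window on or after the operation day = max(0, 53 − *s*). Days strictly after it = max(0, 52 − *s*).

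| Surgery day | On or after the operation | Strictly after |
|---|---|---|
| 29 | 24 | 23 |
| 36 | 17 | 16 |
| 43 | 10 | 9 |
| 50 | 3 | 2 |
| 52 | 1 | 0 |
| 53 to 71 | 0 | 0 |

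The ±1-day dosing window changes each count by at most 1.

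**Range of exposed dates.** Of the possible surgery days after the last dose (Day 23 to Day 71, 71 − 23 + 1 = 49 days), 52 − 23 + 1 = 30 fall on or before Day 52. This counts calendar days and does not predict when surgery will happen.

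**Early stopping.** If only the Day 1 dose is given, the window ends on Day 1 + 30 = Day 31. If Day 15 entinostat is the last dose, it ends on Day 15 + 30 = Day 45. Fewer surgery dates then overlap.

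**Are the data there to separate the two?** Section 7.1.5 records start and stop dates, grade and relation to study drug. The surgery date is needed for the 10-week rule. The gap is therefore in the tabulation, not in the collection.

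**The case against.** **An all-cause 30-day table is a conventional choice.** It avoids subjective attribution in an open-label trial, and perioperative harm after preoperative immunotherapy arguably belongs to safety and feasibility. Section 5.4 adds that immune-related events can appear months after the last dose. This stands, and is why the all-cause table should stay. It does not explain why that table should be the only one.

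**Separation is partly possible already.** If the tables list CTCAE terms, procedure-specific complications can be recognised. This also stands. What stays ambiguous are terms that both drug and surgery can produce, such as anemia or urinary infection. Section 10.3 does not forbid extra tables, but it does not plan them either.

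Some stronger readings are tempting, and the documents do not support them:

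- *That serious operative complications enter the tables for any surgery date.* Section 9.1.1 collects "All AEs meeting serious criteria, from the time of treatment through 90 days following cessation of study treatment" (30 days if new anticancer therapy starts), while Section 9.2.1 says for serious events in general that "recording of the event must begin from day 1 of study treatment and continue through the 30-day follow-up period after treatment is discontinued". That difference concerns reporting. Endpoint 3.2.3 fixes the toxicity evaluation at 30 days, and that is the endpoint Section 10.3 tabulates.
- *That the post-surgery visit brings operative events in wholesale.* After cystectomy that visit comes at 4 to 8 weeks, so it falls after Day 52 for any cystectomy after Day 24 (24 + 28 = 52). For maximal TURBT, at 2 to 4 weeks, it can fall inside the window only for surgery by Day 38 (38 + 14 = 52). Section 8.2.1 asks there specifically for treatment-related serious events and events of clinical interest, and the Time and Events Table has no toxicity assessment on the day of surgery. The route in is the general 30-day reporting duty.
- *That the laboratory tables are equally affected.* Scheduled safety labs end at the pre-surgery visit, so those tables are largely untouched.

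**Conclusion.** The point holds as a limited, inexpensive improvement. Followed as written, Section 10.3 allows an operative complication to become a subject's worst grade whenever surgery falls on or before about Day 52. For surgery from Day 53, no new operative event falls in the 30-day tables.

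This rests on a Day 22 last dose, on reading 3.2.3 as running through 30 days, and on reading the missing qualifier in Section 10.3 as all-cause. The last follows from 3.2.3 and the definition in 9.1.1; Section 10.3 does not use the term.

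The overlap in days is exact for a given surgery date. The effect on grade frequencies is unknown, because the documents give neither a distribution of surgery dates nor operative event rates. A reader might infer from 30 exposed days out of 49 that most subjects are affected, or that the comparison between arms is biased. Neither follows: the first treats a calendar count as a forecast, and no between-arm safety test is planned. The tables are descriptive, and the primary analysis, sample size and surgery-delay stopping rules are unaffected.

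**What to change.** In Section 10.3, keep the all-cause worst-grade table over the 30-day window and add two tables:

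1. A treatment-related worst-grade table by arm over the same window. This keeps drug-related events that start after surgery but within the window.
2. The all-cause table split by onset: before surgery, versus on or after the day of surgery. A subject with no operation stays in the first part for the whole window.

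The cost is a few lines of text and some extra descriptive output, with no new data. There are two downsides. With 20 subjects (10 per arm) many cells will be very small. Open-label attribution is subjective, so the related-only table should be read beside the all-cause one and not replace it.

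Three refinements are optional: showing the on-or-after part separately for cystectomy and maximal TURBT; giving separate pre- and post-surgery grades for an event that starts before surgery and worsens after it (recording of each grade change is stated only in Appendix F, 13.6.4); and summarising the length of the pre-surgery period by arm.

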7.1.6 Disease Assessment

Baseline disease assessment should be obtained within 4 weeks prior to treatment initiation. Assessment of disease will then occur during follow-up, every 6 months for 3 years.

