8.0 EVALUATIONS AND ASSESSMENTS

8.1 Time and Events Table

Assessments	Screening ²		Trea	tmen	t ¹	Pre-		Post-	Follow-
Assessments	Screening	D1	D8	D15	D22	Surgery ¹²	Surgery ¹	Surgery ¹³	up ¹⁴
Informed consent	×								
History	×	×			×	×12		×	
Physical exam	×	×			×				
Performance status	×	×							
Tumor imaging ³	×								×
Pregnancy test ⁴	×				×				
Hematology ⁵	×	×	×	×	×	×			
Serum chemistries ⁶	×	×	×	×	×	×			
Thyroid panel ⁷	×					×			
PT/INR	×					×			
Toxicity assessment	×	×	×	×	×	×12		×	
Concomitant medications	×	×	×	×	×	× ¹²	×		
Pembrolizumab IV		×			×				
Entinostat PO ⁸		×	×	×					
Archival tissue collection ⁹	×								
Blood sample for correlatives ¹⁰		×	×		×		×15		
Fresh tissue collection							×		
Urine collection	×					×			
Buccal swab ¹¹	×								
Survival									×

Footnotes to Time and Events Table

- 1. A window of ±1 day will be applied to study visits on Day 1, Day 8, Day 15 and Day 22. Post-treatment surgery refers to radical cystectomy or maximal TURBT and should occur within 10 weeks from the time of initiation of study therapy.
- 2. Unless otherwise noted, laboratory evaluations may be performed up to 10 days prior to first dose of the clinical trial treatment. Laboratory assessments on day 1 do not need to be repeated if screening labs were performed less than 72 hours prior to the scheduled visit.
- 3. Tumor imaging should include MRI scan or contrasted CT of abdomen and pelvis and CT scan of the chest within 4 weeks prior to treatment initiation and during follow up..
- 4. Serum βhCG must be performed within 72 hours prior to pembrolizumab administration for women of childbearing potential.
- 5. Hematology must include complete blood count with white blood cell differential.
- 6. Serum chemistry must include: sodium, potassium, chloride, CO₂, BUN, creatinine, glucose, calcium, albumin, total protein, total bilirubin, AST, ALT, alkaline phosphatase, magnesium, phosphorus.
- 7. Free T₄ and free or total T₃ will only be measured if TSH is abnormal or if there is a clinical suspicion of an AE related to the endocrine system.
- 8. In Arm 2 only. Entinostat should be taken before the pembrolizumab infusion.
- 9. Fixed paraffin-embedded blocks or slides from the diagnostic TURBT specimen must be requested for subjects at baseline. Sample collection, storage, and shipment instructions for tumor tissue samples are provided in the Laboratory Manual.

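### Section 10.3 plans a clinical complete response (cT0) rate for cystectomy subjects, where it is undefined, and no analysis of the pathologic complete response (pT0N0M0) that is their named secondary endpoint

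*Combined protocol and SAP*

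**What the plan says.** Three parts of the combined protocol and SAP bear on this.

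- **Cystectomy subjects.** Objective 2.2.4 asks for two rates: pathologic response (<pT2) and the "pathologic complete response rate (pT0) after treatment with pembrolizumab alone" and after the combination. Endpoint 3.2.4 fixes the second: "pathologic complete response will be defined as pT0N0M0 at the time of cystectomy".
- **Trimodality subjects.** Objective 2.2.5 asks for the cT0 rate "in patients undergoing maximal TURBT prior to chemoradiation". Endpoint 3.2.5 reads: "The clinical complete response rate (cT0) is defined as cT0 at the time of maximal TURBT".
- **Analysis.** Section 10.3 plans the <pT2 proportion with a 95% confidence interval for cystectomy subjects. It then says that "the proportion of patients who have a clinical complete response (cT0) will be reported separately for those undergoing cystectomy and trimodality therapy". Patients who progress before surgery or have no surgery stay in the estimate and count as not downstaged. Neither pT0 nor pathologic complete response appears in the section.

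**The concern.** The analysis section and the endpoint definitions disagree about what a complete response is in cystectomy subjects. The protocol treats the two terms as different quantities: the abbreviation list gives pT0 as complete pathologic response, and section 3.2.5 defines cT0 separately as a clinical finding at TURBT.

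An analyst who follows section 10.3 must report a rate that has no definition in this group and has no instruction to report the rate that does. An analyst who quietly substitutes pT0N0M0 departs from the written plan. Pathologic complete response is also the activity measure that the protocol's own background (section 1.3.2) cites from neoadjuvant checkpoint-inhibitor studies, and section 10.3 says the results are meant to inform the sizing of future work.

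**Working it through.** The plan gives no computed figure on this point, so the check sets the sections side by side.

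| Proportion | Defined in 3.2.4–3.2.5? | Planned in 10.3? |
|---|---|---|
| <pT2 at cystectomy | Yes (3.2.4) | Yes, with 95% CI |
| pT0N0M0 at cystectomy | Yes (3.2.4) | No |
| cT0, cystectomy subjects | No | Yes |
| cT0, trimodality subjects | Yes (3.2.5) | Yes |

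Defined: 3. Planned: 3. In both: 2. Defined but not planned: 3 − 2 = 1. Planned but not defined: 3 − 2 = 1.

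**Could cT0 be derived for cystectomy subjects anyway?** Criterion 4.1.6 bases clinical T stage on a TURBT sample and imaging.

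1. *TURBT.* The post-treatment procedure for these subjects is the cystectomy. No maximal TURBT is planned for them.
2. *Imaging.* Section 7.1.6 sets a baseline assessment and continues: "Assessment of disease will then occur during follow-up, every 6 months for 3 years". Footnote 3 of the Time and Events Table agrees, placing the "CT scan of the chest within 4 weeks prior to treatment initiation and during follow up". The tumor imaging row is marked in 2 columns, Screening and Follow-up, with 0 marks between them.

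Neither source of a post-treatment clinical stage before cystectomy is scheduled.

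**Could pT0N0M0 be derived?** Section 8.2 has "tissue released for correlative studies post pathological review", so the specimen is reviewed by pathology. The <pT2 endpoint, which section 10.3 does plan, is defined in 3.2.4 as pT0–T1N0M0. It needs the same T, N and M categories as pT0N0M0.

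**Scale of the missing estimate.** The documents do not give the surgical split, so take 5 to 20 cystectomy subjects as an assumption. With no pT0 cases observed, the upper exact 95% limit is 1 − 0.025^(1/n):

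- n = 5: 52%
- n = 10: 31%
- n = 15: 22%
- n = 20: 17%

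The estimate is descriptive and imprecise whichever way the text is corrected.

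**The case against.** The strongest reply is that this is a one-term slip with little consequence. Sections 2.2.4 and 3.2.4 remain in force and give the category, population and time point for pT0. The neighbouring <pT2 analysis supplies the method, and no test or decision depends on the result. Section 10.3 is also not exhaustive: it names no analysis for TCR clonality, neoantigen load or histone acetylation either. The point about consequence stands and limits the severity. It does not remove the fault. Section 10.3 is not merely silent on pT0; it assigns a different, undefined measure to the same subjects. Nor does the <pT2 proportion fill the gap, since it counts pT0 cases without reporting their rate.

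A second objection is that trimodality subjects also have no imaging between screening and follow-up, so the imaging gap does not separate the groups. That is right as far as it goes. What separates them is the maximal TURBT, at which section 3.2.5 places cT0. The imaging gap matters for cystectomy subjects because it closes the only other route.

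A third is that pathology review does not prove that T, N and M are captured as trial data, and section 8.2 provides for lymph node tissue only if available. Any such shortfall would affect the planned <pT2 endpoint equally, so correcting the text creates no new data requirement.

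Finally, reporting by arm and grouping by planned surgery go beyond the pT0/cT0 mismatch. They are offered below as separate clarifications.

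**Conclusion.** The concern holds. Section 10.3 contradicts sections 2.2.4, 2.2.5, 3.2.4 and 3.2.5: one of three defined response proportions has no specified analysis, and one of three planned proportions has no definition. This is an error in the stated analysis of a descriptive secondary endpoint and should be fixed. The primary endpoint, the sample size of 10 per arm and the stopping rule for delayed surgery are not affected. The conclusion rests on the current text of those sections. That pT0N0M0 needs no extra data assumes only that the staging required for the <pT2 endpoint is recorded.

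**What to change.** Replace the response sentences in section 10.3 with wording such as:

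> In the radical cystectomy group, the proportions with <pT2 and with pT0N0M0 at surgery will each be given with a 95% confidence interval. In the trimodality group, the proportion with cT0 at maximal TURBT will be given with a 95% confidence interval.

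Two clarifications are worth making in the same edit:

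1. Give the proportions by treatment arm, which is how objectives 2.2.4 and 2.2.5 read.
2. State that the existing rule for subjects who progress before surgery or have none applies to all three proportions, with groups defined by planned surgery. Section 10.3 now speaks of subjects who undergo cystectomy yet keeps subjects without surgery in the estimate; grouping by plan makes the denominator consistent with that rule.

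The cost is a one-paragraph wording change, with no added visits or assessments.
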